7.6. Strategy of selection of variables in multivariate models

- The strategy of selection of variables in multivariate models will be as follows:
 - Identifying baseline patient characteristics significantly associated with survival time in univariate analyses with a p-value of 0.25.
 - All these variables will be included in the model and a backward elimination will be realized (Starting with a complex model and removing terms sequentially until a final model with only explicative variables significantly associated with the survival time, adjusted each other).

8. Statistical Analysis

This chapter presents the planned statistical analyses to meet the study objectives.

8.1. Efficacy analyses

8.1.1. Survival analyses

▪ Role:

- To meet primary and secondary objectives
- To assess the impact of SU as a first line therapy on progression free survival (PFS) and on time to treatment failure (TTF) for patients with adv/mRCC in real life setting;
- To assess the impact of the SU–other sequence on combined PFS and TTF for patients with adv/mRCC.
- To assess the Overall Survival (OS) (OS median and 24-month OS) for adv/mRCC patients receiving SU in first line followed by other sequence in 2nd line;
- To assess the time to strategy failure (TSF) for adv/mRCC patients receiving the SU–other sequence;
- To assess PFS and OS for the combined 1st line SU – 2nd line sequences according to the second line post SU (TKI, mTOR) treatment; (specific objective – “SU – TKI/mTOR” patients)

▪ Population:

- “SU – other sequence” patients
- “SU – TKI / mTOR” patients

▪ Endpoints:

- Progression Free Survival (PFS)
- Combined PFS
- Time to Treatment Failure (TTF)
- Combined TTF
- Time to Strategy Failure (TSF)

- Overall Survival (median OS and 24-month OS rate)
- **Subgroups:**
- Type of 2nd line treatment post SU: “SU – TKI / mTOR” patients (**SUT-TKI and SUT-mTOR**)
(only combined PFS and OS endpoints)
- **Statistical methods:** Survival analysis methods.
- **Method for handling missing values:** see guideline in chapter 7.

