8.1.2. Objective response rate

- **Role:**
- To assess the Objective Response Rate (ORR) for adv/mRCC patients receiving 2nd line post SU”
- **Population:**
Study population “SU – other sequence” patients
- **Endpoints:**
- Clinical Benefit Rate (CBR)
- Objective Response Rate (ORR)
- **Statistical methods:**
Descriptive analyses
- **Method for handling missing values:**
Hot-deck imputation method and imputation by extreme values

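### SAP 8.1.1 names no first-line sunitinib population for the primary PFS and TTF, and the only label left for them is undefined in the visible text and reads most naturally as a post-sunitinib cohort

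*SAP*

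**What the plan says.** SAP 8.1.1 handles the primary and the sequence endpoints in one block. Its Role opens with the primary objective, "To assess the impact of SU as a first line therapy on progression free survival (PFS) and on time to treatment failure (TTF", and both endpoints are listed. The Population field then gives two labels only:

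- *SU – TKI / mTOR*. The Subgroups entry for these patients adds the limit "only combined PFS and OS endpoints".
- "SU – other sequence” patients".

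Elsewhere in the same Role, overall survival is for patients "receiving SU in first line followed by other sequence in 2nd line", and another line reads "To assess the time to strategy failure (TSF) for adv/mRCC patients receiving the SU–other sequence". SAP 8.1.2 states its role as "To assess the Objective Response Rate (ORR) for adv/mRCC patients receiving 2nd line post SU" and gives the population as "Study population “SU – other sequence” patients". For missing values, 8.1.1 says "see guideline in chapter 7".

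The protocol's primary endpoints (3.3.3) are PFS in patients receiving SU and TTF for first-line SU. Patients are enrolled when they start first-line SU (protocol 8.1).

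**The concern.** Once the TKI/mTOR label is set aside, the primary endpoints have one possible population, and its name describes a treatment sequence. If it means patients who have gone on to something after SU, patients still on SU at the data cut are left out. Depending on the definition, so are those who died on SU or never received a second line. Membership would then be decided by something that happens after the time origin (first SU dose) and is closely tied to the outcome: for TTF, stopping SU is the event itself. Every patient analysed would have the TTF event and none would be censored. The result would no longer describe first-line SU in the enrolled population, which is what the protocol sets out to estimate.

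**Working it through.** **1. What the label can mean**

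| Place | Bearing on *SU – other sequence* |
|---|---|
| SAP 8.1.1 Role | Post-SU: used for combined PFS/TTF and TSF; the OS line has SU followed by a second line |
| SAP 8.1.2 Role | Post-SU: paired with patients receiving second line |
| SAP shell 9.1 | Post-SU: a separate column from *SU 1st line* |
| SAP 8.3 | Post-SU: a separate *SU* label exists, and 8.1.1 does not use it |
| SAP 8.1.2 and 8.2 | Broad: both put *Study population* before the label |
| SAP 2.2 | Broad: follow-up continues whatever comes after SU, including supportive care |
| SAP 8.1.1 Population | Broad: a label meaning only active second line would largely repeat *SU – TKI / mTOR* |

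**2. What the post-SU reading conflicts with**

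- Protocol 3.3.3 and 8.1: primary endpoints and enrolment are defined from the start of SU.
- SAP section 6: everyone is in the primary survival analysis, with incomplete follow-up right-censored.
- SAP shell 9.3: it has a *First line SU* column for PFS and TTF.
- SAP 4.1: the efficacy set has no second-line condition. Section 8.1.1 cites none of the 4.1 sets.

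**3. The plan's own figure**

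The documents size nothing on PFS or TTF. The stated basis is the first-line ORR (protocol 8.7): n = 1.96² × 0.37 × 0.63 / 0.08² = 139.9, so 140. This reproduces, and it presumes that all 140 SU starters are analysed.

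**4. Illustration for TTF**

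Inputs from the protocol: median SU duration m = 5.9 or 10.5 months (6.1.1, community and academic series); 36 months from first visit to last visit (section 5) with 12 months of inclusion (8.1), so 24–36 months of follow-up; treatment visits continue until SU is stopped (8.5.3). Assumptions: exponential SU duration, uniform entry.

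Let λ = ln 2 / m, which is 0.1175 or 0.0660 per month. The share still on SU at the cut is (e^(−24λ) − e^(−36λ)) / (12λ):

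- m = 5.9: (0.0596 − 0.0146) / 1.410 = 0.032, so the share stopped is s = 0.968 (135.5 of 140).
- m = 10.5: (0.2051 − 0.0929) / 0.792 = 0.142, so s = 0.858 (120.2 of 140).

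*Cohort = everyone who stopped SU.* The median x solves 1 − e^(−λx) = s/2, so x = −ln(1 − s/2)/λ:

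- m = 5.9: −ln(0.516)/0.1175 = 5.6 months (−5%).
- m = 10.5: −ln(0.571)/0.0660 = 8.5 months (−19%).

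If follow-up were only 12–24 months (12-month inclusion with the 1-year minimum), s would be 0.869 and 0.687, and the medians 4.9 and 6.4.

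*Cohort = second-line recipients.* The documents give no share reaching second line. Assume 70% of those stopping at 3 months or later reach it, and a share *a* between 0 and 70% of those stopping earlier. With r = a/0.70 and F₃ = 1 − e^(−3λ) (0.297 or 0.180), the median solves 1 − e^(−λx) = [s + (1 − r)F₃]/2. Only the ratio r matters.

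| Early stoppers reaching second line | True 5.9 reads | True 10.5 reads |
|---|---|---|
| 70% | 5.6 | 8.5 |
| 50% | 6.4 | 9.2 |
| 30% | 7.2 | 9.9 |
| 0% | 8.5 | 11.1 |

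For example, at 0% and m = 5.9: (0.968 + 0.297)/2 = 0.633, and −ln(0.3675)/0.1175 = 8.5.

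**5. PFS**

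The same two forces oppose each other. Losing event-free patients still on SU shortens the estimate. Losing patients who died on SU, or failed early and got no second line, lengthens it. The documents do not give the shares needed for a figure.

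**The case against.** The strongest reply is that the plan, read as a whole, points to an analysis of all SU patients. The 8.1.1 Role names first-line SU, section 6 includes everyone, shell 9.3 has the right column, and the 4.1 efficacy set carries no second-line condition. Much of SAP 4.2 to 5.3 is not visible. TSF and the clinical benefit rate also appear without a visible definition, so defining text may well have stood there. The chapter 7 reference looks like a numbering shift, since SAP 5.4 likewise cites appendix 11.1 for what is now 10.1. If so, 8.1.1 sends the reader to the all-patients rule in section 6.

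Most of this stands. The absence of a definition cannot be held against the plan, and the cross-reference is clerical. What remains is that the one section planning the primary analysis has a Population field without a first-line entry. A broad definition in the hidden text would still leave the second-line role in 8.1.2 and the separate column in shell 9.1 to be reconciled. The supporting places also disagree with each other: 4.1 requires 6 months of follow-up, and section 6 includes everyone.

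Two stronger inferences are tempting. One is that the sponsor chose to restrict the primary analysis to second-line patients. The documents do not show this, and an omitted entry explains the text equally well. The other is that TTF would come out too short. That follows only if the cohort is everyone who stopped SU. Among second-line recipients, early failures who never reach second line drop out, and the median can come out too long.

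**Conclusion.** The point holds as an ambiguity in the primary analysis population that should be settled before analysis. It is not a demonstrated bias. On the whole-study reading nothing is lost and only the wording needs repair. On a post-SU reading the primary cohort is wrong, by an amount that depends on a definition not in view. Under the assumptions above, the shift in median TTF runs from −0.3 to +2.6 months when the truth is 5.9, and from −2.0 to +0.6 when it is 10.5. For scale, the sampling SD of the Kaplan-Meier median with all 140 patients is about 0.7 and 1.3 months (simulation under the same exponential, 24–36 month assumptions). The ranges rest on exponential durations, 24–36 months of follow-up, and assumed shares reaching second line that no document supports. The direction for PFS is likewise open.

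**What to change.** In SAP 8.1.1, define each label and state the population for each endpoint:

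1. **First-line PFS and TTF:** all enrolled patients with at least one SU dose, censored at last assessment if event-free (PFS) or still on SU (TTF). Do not condition on reaching second line. Do not apply the 6-month follow-up condition of the 4.1 efficacy set either, because it too is a post-baseline selection and conflicts with section 6.
2. **Combined PFS, combined TTF, TSF and SU-then-second-line OS:** the sequence cohorts, reported as conditional on reaching second line.
3. **Clerical:** point the missing-values reference to section 6.

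The cost is a few lines of SAP text, with no new data and no new endpoint. Setting aside the 6-month condition for these endpoints is a change of analysis set, not only of wording. It restores the protocol's own population, so no protocol amendment is needed. If a restriction to post-SU patients was really intended, protocol 8.9 would call for an amendment, as a major change to a primary analysis.

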8.1.2. Objective response rate

- **Role:**
- To assess the Objective Response Rate (ORR) for adv/mRCC patients receiving 2nd line post SU”
- **Population:**
Study population “SU – other sequence” patients
- **Endpoints:**
- Clinical Benefit Rate (CBR)
- Objective Response Rate (ORR)
- **Statistical methods:**
Descriptive analyses
- **Method for handling missing values:**
Hot-deck imputation method and imputation by extreme values

8.2. Safety and tolerability analyses

- **Role:**
To describe safety and tolerability of patients receiving the SU–other sequence”.
- **Population:**
Study population “SU – other sequence” patients
- **Endpoints:**
- Incidence of adverse events (AEs)
- Discontinuation
- Deaths
- **Statistical methods:**
Descriptive methods
- **Method for handling missing values:**
None-Observed-case analysis

9.2. Initial dose and schedule of SU in the first line treatment

Initial dose SU	N(%)
50mg	
37.5mg	
25mg	
Other	
Schedule	N(%)
4 weeks on, two weeks off	
Continous	

[figure not shown]
Other	
-------	--

9.3. Cross tabulation of efficacy end points(PFS,OS,ORR,TTF) for both first line SU treatment as well as for the SU- second line therapy

Efficacy endpoints (months±SD)	Overall	First line SU	Second line therapy				
			SU-Bsc	SU-AXI	SU/TOR	SU/TKI	
PFS							
OS							
ORR							
TTF							

9.4. OS based on MSKCC risk stratification

Fig. 1 OS stratified by MSKCC risk classification.

9.5. Cross tabulation of AE experienced throughout the study according to disease grade

N (%) with adverse event	Sunitinib (N = 85)	
	All grades	Grades 3/4
Any adverse event	83 (97.6)	23 (27.1)
Fatigue/Asthenia	69 (81.2)	8 (9.4)
Mucositis/Stomatitis	50 (58.8)	2 (2.4)
Hand-foot syndrome	29 (34.1)	2 (2.4)
Diarrhea	26 (30.6)	0 (0.0)
Hypertension	35 (41.2)	3 (3.5)
Decreased taste sensation	36 (42.4)	0 (0.0)
Abdominal pain	19 (22.4)	3 (3.5)
Nausea	25 (29.4)	3 (3.5)
Lack of appetite	12 (14.1)	0 (0.0)
Pain	13 (15.3)	0 (0.0)
Anorexia	15 (17.6)	5 (5.9)
Vomiting	15 (17.6)	5 (5.9)
Hemorrhage	12 (14.1)	0 (0.0)
Constipation	6 (7.1)	0 (0.0)
Edema	12 (14.1)	1 (1.2)
Dermatitis	6 (7.1)	0 (0.0)
Anemia	5 (5.9)	1 (1.2)
Erythema	7 (8.2)	1 (1.2)
Hypothyroidism	6 (7.1)	1 (1.2)
Skin rash	2 (2.4)	0 (0.0)
Dyspnea	4 (4.7)	0 (0.0)
Hemorrhoids	5 (5.9)	0 (0.0)
Alopecia	1 (1.2)	0 (0.0)

10. Appendices

10.1. Appendix 1: FKSI-19 questionnaire

NCCN-FACT FKSI-19								
		Below is a list of statements that other people with your illness have said are important. Please circle or mark one number per line to indicate your response as it applies to the past 7 days.						
		Not at all	A little bit	Some-what	Quite a bit	Very much		
D R S- P	GP1	I have a lack of energy	0	1	2	3	4	
	GP4	I have pain	0	1	2	3	4	
	C2	I am losing weight	0	1	2	3	4	
	H17	I feel fatigued.....	0	1	2	3	4	
	B1	I have been short of breath	0	1	2	3	4	
	BRM3	I am bothered by fevers (episodes of high body temperature).....	0	1	2	3	4	
	BP1	I have bone pain	0	1	2	3	4	
	L2	I have been coughing.....	0	1	2	3	4	
	H112	I feel weak all over	0	1	2	3	4	
	RCC 2	I have had blood in my urine.....	0	1	2	3	4	
D R S- E	C6	I have a good appetite.....	0	1	2	3	4	
	GF5	I am sleeping well.....	0	1	2	3	4	
	GE6	I worry that my condition will get worse	0	1	2	3	4	
	GP2	I have nausea	0	1	2	3	4	
	T S E	C5	I have diarrhea (diarrhoea)	0	1	2	3	4
	GPS	I am bothered by side effects of treatment	0	1	2	3	4	
	F W B	GF1	I am able to work (include work at home)	0	1	2	3	4
	GF3	I am able to enjoy life.....	0	1	2	3	4	
	GF7	I am content with the quality of my life right now.....	0	1	2	3	4	

DRS-P=Disease-Related Symptoms Subscale – Physical
 DRS-E=Disease-Related Symptoms Subscale – Emotional
 TSE=Treatment Side Effects Subscale
 FWB=Function and Well-Being Subscales

Source: www.facit.org

10.2. Appendix 2: FKSI-19 (version 4) – Scoring guidelines

Instructions:

1. Record answers in "item response" column. If missing, mark with an X
2. Perform reversals as indicated, and sum individual items to obtain a score.
3. Multiply the sum of the item scores by the number of items in the subscale, then divide by the number of items answered. This produces the symptom index score.
4. As with all FACIT questionnaires, a high score is good. Therefore, a score of "0" is a severely symptomatic patient and the highest possible score is an asymptomatic patient.

Note: If >50% of items were completed, the FKSI scores were calculated as the sum of the item responses divided by the number of items completed multiplied by the total number of items in the scale (eg, 19 in the case of the FKSI-19).

If fewer than 50% of the items were completed, the scores were considered missing.

Scale	Item Code	Reverse item	Item response	Item Score
FKSI-19	GP1	4	-	= _____
Total	GP4	4	-	= _____
Score range: 0-76	C2	4	-	= _____
	HI7	4	-	= _____
	B1	4	-	= _____
	BRM3	4	-	= _____
	BP1	4	-	= _____
	L2	4	-	= _____
	HI12	4	-	= _____
	RCC2	4	-	= _____
	C6	0	+	= _____
	GF5	0	+	= _____
	GE6	4	-	= _____
	GP2	4	-	= _____
	C5	4	-	= _____
	GP5	4	-	= _____
	GF1	0	+	= _____
	GF3	0	+	= _____

GF7 0 + _____ = _____

Sum individual item scores: _____

Multiply by 19: _____

Divide by number of items answered: _____ = **FKSI-****19 score**

Subscale	Item Code	Reverse item	Item response	Item Score
FKSI-DRS-P	GP1	4 -	_____	= _____
(Disease Related	GP4	4 -	_____	= _____
Symptoms-Physical)	C2	4 -	_____	= _____
Score range: 0-48	HI7	4 -	_____	= _____
	B1	4 -	_____	= _____
	BRM3	4 -	_____	= _____
	BP1	4 -	_____	= _____
	L2	4 -	_____	= _____
	HI12	4 -	_____	= _____
	RCC2	4 -	_____	= _____
	C6	0 +	_____	= _____
	GF5	0 +	_____	= _____

Sum individual item scores: _____

Multiply by12: _____

Divide by number of items answered: _____ = **FKSI-****DRS-P score**

Subscale	Item Code	Reverse item	Item response	Item Score
FKSI-DRS-E				
(Disease Related				
Symptoms-Emotional)	GE6	4 -	_____	
Score range: 0-4	= _____	=	FKSI-DRS-E	

score

Subscale	Item Code	Reverse item	Item response	Item Score
FKSI-TSE (Treatment Side Effects)	GP2 C5 GP5	4 - 4 - 4 -	_____ _____ _____	= _____ = _____ = _____

Score range: 0-12

Sum individual item scores: _____

Multiply by 3: _____

Divide by number of items answered: _____ = FKSI-TSE

score

Subscale	Item Code	Reverse item	Item response	Item Score
FKSI-F/WB (Function/ Well-Being)	GF1 GF3 GF7	0 + 0 + 0 +	_____ _____ _____	= _____ = _____ = _____

Score range: 0-12

Sum individual item scores: _____

Multiply by 3: _____

Divide by number of items answered: _____ = FKSI-F/

WB score

Appendix 3: List of covariate and outcomes in the study

Variable	Role	Operational definition
Age	Covariate	Defined as the date of birth of the participant
Gender	Covariate	Defined as the male or female sex
Ethnicity	Covariate	Defined as race of Middle Eastern, Indian, Caucasian or African descendant
ECOG	Covariate	The ECOG Scale of Performance Status describes a patient's level of functioning in terms of their ability to care for themselves, daily activity, and physical ability (walking, working, etc.)
Number of metastatic sites	Covariate	Total number of site where metastasis is detected
Nephrectomy	Covariate	Surgical removal of the kidney
MSKCC risk	Covariate	The MSKCC risk system stratifies patients with mRCC into poor-, intermediate- and favorable-risk categories based on the number of adverse clinical and laboratory parameters present
Hypertension	Covariate	Presence of high systolic blood pressure >13mmHg
Previous medical treatment	Covariate	Presence of medical treatment related to the disease prior to SU initiation
PFS	Outcome	The PFS will be defined as the time from when the patient receives the first dose of SU to the time of progression or death due to any cause, whichever occurs first
OS	Outcome	OS defined as the time from date of first SU dose to the date of death of any cause.
ORR	Outcome	The objective response rate is the percentage of patients with a complete response (CR) or a partial response (PR) according to RECIST 1.1 criteria as best response, over the SU treatment period.
TTF	Outcome	TTF is defined as the time from when the patient receives the first dose of treatment to the date of SU discontinuation
Combined PFS	Outcome	The time from when the patients receives the first dose of SU as first line, until progression or death due to any cause while on the 2nd line treatment, whichever occurs first during the 2nd line sequence treatment.
Combined TTF	Outcome	The time from when the patient receives the first dose with SU as first line, to the time of 2nd line sequence discontinuation

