3.3.3. End-points

Primary End-point:

1. Progression Free Survival (PFS) for patients with ad/mRCC receiving SU.

PFS is defined as: the time from when the patient receives the first dose of SU to the time of progression or death due to any cause, which occurs first.

2. Time to Treatment Failure (TTF) for SU 1st line.

TTF is defined as: from when the patient receives the first dose of SU to the time of SU discontinuation (date completed by the physician).

Secondary End-point:

1. Objective Response Rate (OOR) for adv/mRCC patients receiving SU as 1st line treatment.

ORR is defined as the percentage of patients with confirmed CR or confirmed PR according to RECIST criteria v1.1.

2. Description of SU real life usage of doses across all centers, including description of treatment schedules (dose change, dose schedule, average dose received during the period treatment).

3. Combined PFS for patients with ad/mRCC receiving the 2nd line sequence SU- different treatment.

Combined PFS is defined as: the time from when the patients receives the first dose of SU as first line, until progression or death due to any cause while on the 2nd line treatment, whichever occurs first during the 2nd line sequence treatment.

4. Combined TTF for the SU-2nd line sequence.

Combined TTF is defined: as the time from when the patient receives the first dose with SU as first line, to the time of 2nd line sequence discontinuation (date completed by the physician).

5. OS for adv/mRCC patients receiving SU as first line followed by 2nd line as measured from date of first SU dose to the date of death of any cause. The OS median and the overall survival at month 24 (24 months OS) will be measured.
6. If possible, efficacy parameters (PFS, OS) for the combined 1st line SU- 2nd line sequences according to the second line post SU (other than SU-AXI):
 - SU in 1st line-Axitinib TKI in 2nd line.
 - SU in 1st line- other TKI in 2nd line (sorafenib, pazopanib).
 - SU in 1st line/mTOR in 2nd line (temsirolimus, everolimus).
7. Safety description with AE listing in patients receiving SU: frequencies of patients experiencing at least one AE will be displayed by body system.
8. QoL using the questionnaire Functional Assessment of Cancer Therapy-Kidney Symptom Index 19 (FKSI-19).

CCI

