8.7. Sample Size

Due to the non-existence of a sample size calculation/justification for estimating the median progression free survival in phase IV trials and the exploratory/observatory nature of this study, we opt not to base the sample size on the main objective. However, we will use the secondary objective of estimation of the ORR for adv/mRCC patients receiving SU in the 1st line as the basis of the sample size. With 140 patients we will be able to assess the ORR to within a margin of error of at most $\pm 8\%$ using 95% confidence intervals. This is based on the assumption that the ORR will be less than 37% as per the literature.^{12,25} This sample size is also within the range of sample sizes of other studies investigating SU for first line and where PFS and TTF were estimated.²⁵

The 140 patients will be enrolled at 14 sites in the Middle Eastern & African countries; namely UAE, Qatar, RSA, Egypt, Algeria, Tunisia and Morocco. Each site is expected to enroll an average of 10 patients. This will ensure diverse and possibly representative sample of the Middle East and North Africa region.

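### ORR requires a confirmed response in the protocol, but SAP Appendix 3 does not mention confirmation, so the SAP rate is at least as high and the two definitions need aligning

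*SAP*

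**What the plan says.** Protocol 3.3.3, secondary end-point 1: "ORR is defined as the percentage of patients with confirmed CR or confirmed PR according to RECIST criteria v1.1".

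The ORR row of SAP Appendix 3, in the column of operational definitions, counts a CR or a PR under RECIST 1.1 "as best response, over the SU treatment period". Confirmation is not mentioned.

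Protocol 8.7 makes ORR the basis of the sample size: "we will use the secondary objective of estimation of the ORR for adv/mRCC patients receiving SU in the 1st line". It gives 140 patients, a 95% margin of at most 8 percentage points, and an assumed ORR below 37%. It does not say whether the 37% is a confirmed or a best-response rate.

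Protocol 8.2 expects tumour assessments roughly every 3 months, following clinical practice. Protocol 8.5 leaves the eCRF blank where an item was not collected. Neither document sets a confirmation interval or a rule for deciding that a response is confirmed, in the text available.

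**The concern.** The two rules classify some patients differently. A patient with a PR on one scan, and no later scan that still shows response, is a responder under Appendix 3 read as written and a non-responder under Protocol 3.3.3. With scans about 3 months apart and no scan required by the study, such patients are foreseeable: some will progress, stop SU, die or reach the end of follow-up before a second assessment.

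ORR is the only endpoint for which the protocol states a precision. The same responder flag feeds the optional logistic model (Protocol 8.9, SAP 7.3) and the missing-data rules for ORR (SAP section 6). Two programmers, one working from each document, could derive different flags from the same data, and a reader of the report could not tell which ORR was shown.

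**Working it through.** **Inputs.** N = 140, margin 8 points, 95% confidence, ORR ceiling 37% (Protocol 8.7); Clopper-Pearson interval for ORR (Protocol 8.9, SAP 7.1). The share u of best responders whose response is not confirmed is in neither document; 0 to 25% is an assumption.

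**1. The plan's own figure.** With the normal approximation:

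- half-width = 1.96 × √(0.37 × 0.63 / 140) = 0.0800, or 8.00 points;
- N for 8 points = 1.96² × 0.37 × 0.63 / 0.08² = 139.9, rounded up to 140.

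The stated figure reproduces.

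**2. Direction.** Every patient with a confirmed CR or PR also has CR or PR as best response. With the same patients and window, the confirmed responders are therefore a subset of the best-response responders, and the SAP rate cannot be below the protocol rate. The two are equal if every response is confirmed. Each unconfirmed responder adds 1/140 = 0.7 point to the SAP rate.

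**3. Size.** The gap is u × best-response rate. Take 52/140 = 37.1% as the best-response rate and round to whole patients:

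| Assumed u | Confirmed responders | Confirmed ORR (Clopper-Pearson 95% CI) | Gap, points |
|---|---|---|---|
| 0% | 52 | 37.1% (29.1 to 45.7) | 0 |
| 10% | 47 | 33.6% (25.8 to 42.0) | 3.6 |
| 20% | 42 | 30.0% (22.6 to 38.3) | 7.1 |
| 25% | 39 | 27.9% (20.6 to 36.1) | 9.3 |

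The protocol expects an ORR below 37%, so this is near the top of its range. At an illustrative best-response rate of 35/140 = 25%, the gap is 0.10 × 25 = 2.5 points at u = 10% and 0.25 × 25 = 6.3 points at u = 25%.

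**4. Sizing.** The precision statement is conditional on an ORR below 37% and holds for whichever definition meets that condition. If 37% bounds the best-response rate, the confirmed rate is no higher and the half-width is at most 8.00 points (7.43 at 39/140). If 37% is instead a confirmed rate and best response is reported, u = 25% gives 0.37/0.75 = 49.3% and a half-width of 8.28 points. That is practically the maximum for any rate at N = 140, since 1.96 × √(0.25/140) = 0.0828. Nothing here calls for a different N. The Clopper-Pearson half-width at 52/140 is 8.29 points, slightly over 8; that comes from the interval method, not from the response definition.

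**The case against.** The strongest defence has four parts.

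- **The SAP is allowed to differ.** Protocol 8.3 leaves detailed variable definitions to the SAP. Protocol 8.9 lets the SAP modify the protocol's plans and calls for an amendment only for major changes to primary endpoints, whereas ORR is secondary. This stands. A reader might infer that the two documents cannot both be followed; Protocol 8.9 does not support that, because the SAP may take precedence. But nothing in the available text presents the change as intended.
- **Part of the SAP is not visible.** The endpoint text before section 5.4 is missing from the copy reviewed, which is not a fault of the plan. A confirmation rule there cannot be excluded, nor can it be assumed that Appendix 3 is the only definition programmers would see. Even so, Appendix 3 would then disagree with the SAP's own endpoint section.
- **Best response under RECIST 1.1 might already imply confirmation.** Appendix 3 is silent on confirmation and does not waive it. But the protocol names RECIST 1.1 and also requires confirmation in words; the SAP keeps the first and drops the second. The ambiguity is itself the problem.
- **The size is assumed.** This stands. The documents do not fix u, and zero is possible. The sponsor can also point to Protocol 8.11, which describes the study as hypothesis-generating.

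A different matter, the population named for ORR in SAP 8.1.2 (patients receiving second-line treatment), could move the rate either way. It is outside this comparison, which holds patients and window fixed.

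**Conclusion.** The mismatch is real and should be resolved before ORR is derived. What is established is that Appendix 3, applied as written, gives a rate at least as high as the protocol endpoint for the same patients and window, and higher by 0.7 point per unconfirmed responder. Under the assumed 0 to 25% unconfirmed share and a best-response rate of 37.1%, the gap is 0 to 9.3 points.

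Three stronger readings are tempting and not supported. One is that the SAP rate will certainly be higher: the rates coincide if all responses are confirmed. Another is that the gap is about as large as the 8-point margin: that is true only near the top of an assumed range combined with a response rate near the protocol's ceiling. The third is that the sample size is undermined: 140 reproduces, and the margin does not depend on which definition is used as long as the ORR is below 37%. What is affected is the reported estimate and its meaning.

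**What to change.** Amend the ORR row of SAP Appendix 3, and any endpoint text that repeats it, to the protocol's confirmed definition, and state:

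- confirmation comes from a subsequent routine tumour assessment, with no added visits or scans, and whether that assessment must fall before SU discontinuation;
- all analysed patients stay in the denominator;
- a responder with no later scan counts as unconfirmed, not as missing, so that the SAP section 6 imputation is not triggered for that reason, and the number of such patients is reported;
- best response regardless of confirmation is reported as a labelled supportive rate with its own Clopper-Pearson interval.

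If the sponsor intends best response as the main definition, the SAP should record this as a deliberate change from Protocol 3.3.3, with the reason, and still report the confirmed rate.

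The cost is a short SAP revision and one extra derived variable from data already being collected. The headline ORR may come out somewhat lower. It may also understate response where scans about every 3 months leave no confirming assessment; the supportive rate and the count of responders without a later scan make that visible.
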